Study Protocol and Statistical Analysis Plan

Modulation of the Intestinal Microbiome by a High Protein Diet

NCT04812964

Document date: April 5, 2018

STUDY PROTOCOL: Modulation of the Intestinal Microbiome by a High Protein Diet

A. Design of randomized, controlled study comparing high and normal protein isocaloric calorie restriction diets for obesity.

Rationale and hypothesis: Based on my preclinical rodent model data, I hypothesize that a high protein diet will shift the composition of the microbiome of obese subjects, including increased *Akkermansia*, and that this will be associated with alterations of the metagenome (bacterial genes) and metabolome.

Study design: This hypothesis will be investigated in a randomized controlled study of the intestinal microbiome of an estimated 216 obese Veterans assigned 1:1 to isocaloric high protein (HPD) or normal protein (NPD) diets. The study will be advertised by posting flyers in the West Los Angeles VA Medical Center MOVE obesity clinic. MOVE physicians will provide interested patients with information about the study. Participants will undergo an initial screening visit in the clinical research unit after their MOVE appointment or on a later date. Once enrolled, participants will return to the clinical research unit for a baseline visit and follow-up visits on weeks 2, 4, 6, 8, 12, and 16 for dietary counseling, physical measurements, phlebotomy, and dietary questionnaires. The recruitment rate is estimated as 7 per month based on the recently completed study led by [name]. Patient recruitment and sample collection will be performed during the first 3 years of the study.

Inclusion criteria: Men and women between 20 and 75 years of age, BMI 27 to 40 kg/m², non-smoker or stable smoking habits for at least 6 months prior to screening and agreement not to change such habits during the study; subjects on non-obesity prescription medication may be included.

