Microbiome analysis: DNA will be extracted from fecal samples collected in ethanol at baseline, day 3, day 7, week 2, day 17 (3 days after calorie restriction), day 21 (7 days after calorie restriction), week 4, week 6, week 8, week 12, and week 16 using the MO BIO Powersoil kit. Sequencing of the 253 base pair V4 region of 16S ribosomal DNA will be performed using the Illumina HiSeq 2500 to a depth of 250,000 reads per sample. Microbial diversity (alpha diversity) will be compared between the two dietary groups at each time point using the Chao1 index, Shannon index, and Faith's phylogenetic diversity. Significance will be determined using a non-parametric test (Mann-Whitney U). Microbial composition (beta diversity) will be compared across all samples using weighted UniFrac (a phylogenetic distance metric) and visualized by principal coordinates analysis (PCoA). Significance of differences in composition at each time point will be determined using Adonis, a permutation-based method. Baseline data will be analyzed to confirm that randomization had successfully eliminated pre-existing microbial differences between the two dietary groups.

Abundance of individual bacteria will then be fitted to multivariate models using DESeq2. This algorithm performs normalization using size factors estimated by the median-of-ratios method, employs an empirical Bayesian approach to shrink dispersion, and fits the data to negative binomial models. Diet group, time point, interaction between diet and time point, baseline BMI, age, sex, and smoking status will be covariates in the model. Diet composition parameters derived from the nutritional instruments (3DFR, FFQ) may also be included. This model will be compared to a reduced model that does not include the diet:time point interaction. A likelihood ratio test will be used to identify microbes with differential abundance by diet at time points after baseline. Estimates of significance will be adjusted for multiple hypothesis testing to calculate q-values, which represents the false discovery rate. Q-values less than 0.05 will be considered significant. Microbes that are differentially abundant on a HPD will be grouped by hierarchical clustering to highlight distinct kinetic patterns of microbial change.

D. Risk/benefit analysis

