1. RISKS TO SUBJECTS

a. Human subjects involvement and characteristics

Human subjects will be recruited from the MOVE Obesity Clinic at the West Los Angeles VA Medical Center within the VA Greater Los Angeles Healthcare System (GLAHS). They will be referred for study enrollment if they meet the inclusion criteria and do not meet any provisions of the exclusion criteria. The inclusion criteria include: men and women between 20 and 60 years of age, BMI 27 to 40 kg/m², non-smoker or stable smoking habits for at least 6 months prior to screening and agreement not to change such habits during the study. The exclusion criteria include weight change of > 3.0 kg in the month prior to screening, weight loss of > 10 kg in the 6 months prior to screening, calorie restriction diet (< 1500 kcal/day) for a period of 4 months or more in the 12 months prior to screening, use of any other investigational drug(s) within 8 weeks prior to screening, abnormal baseline laboratory parameters (serum creatinine > 1.6 mg/dl; ALT, AST, total bilirubin > 2.0 times the upper limit of normal; triglycerides > 500 mg/dl, total cholesterol > 350 mg/dl, TSH outside of normal range), consumption of more than 1 alcoholic beverage per day, pregnancy or intention to become pregnant. Following

informed consent, subjects will undergo randomization to either the normal protein diet or high protein diet groups. Both dietary interventions are consistent with clinical practice for management of obesity and do not pose any appreciable risk to the patient. Subjects will be asked to collect stool eleven times and to visit the VA clinical research unit seven times over 16 weeks.

b. Sources of material

Data and materials collected during the study will be used only according to the protocol approved by the VA Institutional Review Board (IRB). All information will be retained electronically behind the VA's electronic firewall except for regulatory documents and printed informed consent forms. All subjects will receive a unique research identifier number with the identities of the subjects retained only in a code key kept in a secure directory behind the firewall. Stool will be collected by techniques described in Aim 1 of the Research Plan. Demographic and medical data will be collected for all of the subjects according to the study protocol. Only the principal investigator (PI, [name]) and study coordinator will have access to confidential patient information.

c. Potential risks

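### Up to 2,376 stools collected over 3 years will need several laboratory batches, but the plan has no batch term, no batch adjustment and no rule for laying out samples, which leaves avoidable noise in the diet comparisons

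*Combined protocol and SAP*

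**What the plan says.** Section A (Study design) plans "an estimated 216 obese Veterans assigned 1:1 to isocaloric high protein (HPD) or normal protein (NPD) diets" and states that "Patient recruitment and sample collection will be performed during the first 3 years of the study". Section D.1.a confirms the sampling burden: "Subjects will be asked to collect stool eleven times and to visit the VA clinical research unit seven times over 16 weeks".

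Section C (Microbiome analysis) lists 11 time points for extraction, starting "DNA will be extracted from fecal samples collected in ethanol at baseline, day 3, day 7, week 2, day 17", and specifies sequencing on the "Illumina HiSeq 2500 to a depth of 250,000 reads per sample". It names the extraction kit, but gives no plate format, number of runs, layout or control samples.

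The DESeq2 terms are set out in full: "Diet group, time point, interaction between diet and time point, baseline BMI, age, sex, and smoking status will be covariates in the model". The only optional additions are diet-composition parameters from the food record and questionnaire. The taxon test is a likelihood ratio test of the diet-by-time interaction. Alpha diversity (Mann-Whitney) and composition (Adonis) are compared between arms at each time point. Section C (Fecal sampling) says that samples are stored at -80°C. It does not say when, or in what grouping, they are processed.

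**The concern.** Extraction and sequencing batches can shift the measured abundance of particular taxa. When one person's samples lie on different plates, each change from baseline carries the difference between two plate effects.

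Nothing in the stated model absorbs that. BMI is taken at baseline, and age, sex and smoking are effectively fixed within a participant over 16 weeks. Median-of-ratios normalization gives one size factor per sample, so it corrects for depth and not for taxon-specific shifts. The diversity and composition tests have no adjustment at all.

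At stake is precision for the trial's stated microbiome hypothesis. The kinetic patterns that the plan intends to cluster are also at risk if batch follows visit. A layout cannot be repaired once the samples have been extracted.

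**Working it through.** **Counts, from the documents.**
- Samples: 216 × 11 = 2,376, the maximum with no dropout or missed stools. The listed time points do number 11.
- Reads: 2,376 × 250,000 = 594 million.
- Timeline: at 7 recruits a month, 216 / 7 = 30.9 months. With 16 weeks of follow-up this is about 34.5 months, which fits 3 years.
- The 216 itself cannot be reproduced, because the documents give no power inputs.

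**Batches (plate format assumed).** 2,376 / 96 = 24.75, so 25 full plates, or 26 to 27 if some wells are kept for controls. Other formats give 7 plates of 384 or 99 batches of 24. All of these mean several batches.

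**Where a participant's samples fall (96 wells, 1,000 simulated layouts).**

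| Layout | Mean plates per participant | Baseline and week 16 on same plate |
|---|---|---|
| Random | 9.1 | 4% |
| Order of collection | 3.9 | almost never |
| Visit by visit | 11.0 | never |
| Participant kept together | 1 | always |

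**Early contrasts in order of collection.** 7 × 11 = 77 samples a month, so a plate spans 96 / 77 × 30.44 = 38 days. Baseline shares a plate with day 7 about 1 − 7/38 = 82% of the time, and with week 2 about 1 − 14/38 = 63%. Let r be plate variance divided by within-person variance. The variance of a change is inflated by 1 + r × (share on different plates). At r = 0.25 this is 1 + 0.25 × 0.18 = 1.05 for day 7, 1 + 0.25 × 0.37 = 1.09 for week 2, and 1.25 for week 16.

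**Loss for a pure within-person change.** The variance 2σ² becomes 2σ²(1 + r), so the information lost is 1 − 1/(1 + r): 9%, 20% and 33% for r = 0.10, 0.25 and 0.50. For a contrast with an illustrative 80% power (two-sided 0.05), the simulated order-of-collection layout gives 76%, 71% and 63%.

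**Loss for the tests as specified.** These also carry between-person variance, taken as B times within-person variance, with B = 1 or 2 (assumed).
- Comparison at one visit: loss = 1 − (1 + B)/(1 + B + r). At r = 0.25 this is 1 − 2/2.25 = 11% or 1 − 3/3.25 = 8%.
- One interaction contrast. The model has no participant term, so its standard error scales with √(1 + B + r), while the estimate varies with √(1 + r). The sample-size factor that keeps 80% power is k = [(1.96√(1+B+r) + 0.84√(1+r)) / (1.96√(1+B) + 0.84)]². At r = 0.25, k = 1.154 (B = 1) or 1.116 (B = 2), and the loss 1 − 1/k is 13% or 10%.

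| r | Within-person change | One visit, B = 1 / 2 | Interaction, B = 1 / 2 |
|---|---|---|---|
| 0.10 | 9% | 5% / 3% | 6% / 4% |
| 0.25 | 20% | 11% / 8% | 13% / 10% |
| 0.50 | 33% | 20% / 14% | 23% / 19% |

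**Visit-by-visit filling.** The interaction contrast suffers less: simulated inflation is 1.06, 1.15 and 1.30 for the three values of r. The average change from baseline to week 16 over both arms is another matter. Per unit of plate variance, its added variance is 0.765, against 2/216 = 0.0093 per unit of within-person variance, a ratio of about 83. Time and plate are then confounded.

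**Participant kept together.** Plate shifts cancel in every within-person contrast, so inflation is 1.00.

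**The case against.** The strongest reply is that silence is not neglect. Plating may have been left to laboratory procedures that are not in these documents. Storage at -80°C, with collection confined to the first 3 years, leaves room for joint processing later. That stands: the documents show that nothing is pre-specified, not that the laboratory would ignore batch.

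Three stronger readings are tempting and are not supported.

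- A reader might infer a loss equal to 20% of 216, about 43 participants. That is the result for a pure within-person change at r = 0.25. The plan compares arms visit by visit and fits a model with no participant term. At the same r, the loss is about 8% to 13%, or 17 to 29 participants.
- A reader might infer that every time contrast is damaged equally. Under order-of-collection processing, baseline and the early samples would often share a plate. Order-of-collection processing is itself a supposition.
- A reader might infer that plate imbalance would create a false diet effect. With 1:1 randomization, chance imbalance of arms across plates is noise on average and not systematic bias.

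It can also be argued that a plate term is redundant once each participant's samples share a plate. For the interaction estimate that is largely so. But with no participant term in the model, the plate term is what takes plate variance out of the dispersion.

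**Conclusion.** The point holds as a gap in pre-specification with a real but moderate cost. The sample count, the collection period, the closed covariate list and the absence of any layout rule are all in the documents. Several batches follow in any usual format; about 25 to 27 plates rests on assuming 96 wells.

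For diet comparisons the harm is mainly lost precision, greatest for late-versus-baseline contrasts. Its size depends wholly on plate and between-person variances that the documents do not give. The range in the table is illustrative and is not an estimate for this trial. The one scenario worse than noise is visit-by-visit filling, which would confound the time course with plate, and the plan does not rule it out. The change is worth making before extraction starts.

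**What to change.** In Section C (Microbiome analysis), specify the following.

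1. Bank samples at -80°C, and confirm that this storage covers the ethanol-fixed cups. Process all of a participant's stools on one extraction plate and in one sequencing run.
2. Balance the arms on each plate in random well order under coded IDs. For example, 8 participants, 4 per arm, fill 8 × 11 = 88 wells and leave 8 spare. This gives 216 / 8 = 27 plates.
3. Add plate (and run, where it is not determined by plate) to both the full and the reduced DESeq2 models.
4. In Adonis, enter plate as the first term and restrict permutations within plate. For alpha diversity, use a plate-stratified rank test.

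The model's own standard errors gain fully from step 1 only if a participant term or a paired analysis is also used, so the two should be considered together.

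Costs: a plating list and the added model terms; extraction of a participant's samples waits for the week 16 stool; about two more plates are used (27 against 25); and about 26 degrees of freedom go to plate, which weighs most in the per-visit Adonis with at most 216 samples.

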Exclusion criteria: Weight change of > 3.0 kg in the month prior to screening, weight loss of > 10 kg in the 6 months prior to screening, calorie restriction diet (< 1500 kcal/day) for a period of 4 months or more in the 12 months prior to screening, use of any other investigational drug(s) within 8 weeks prior to screening, abnormal baseline laboratory parameters (serum creatinine > 1.6 mg/dl; ALT, AST, total bilirubin > 2.0 times the upper limit of normal; triglycerides > 500 mg/dl, total cholesterol > 350 mg/dl, TSH outside of normal range), consumption of more than 1 alcoholic beverage per day, pregnancy or intention to become pregnant.

Consent: Veterans will be consented during their screening visit. They must sign the VA GLAHS Institutional Review Board-approved written informed consent prior to the initiation of any study specific procedures or randomization.

Enrollment and randomization: Date of birth, sex, race, medical history, current medications, smoking and alcohol history will be obtained by the study coordinator during the screening visit. Eligible subjects will be assigned an enrollment number after signing the informed consent form then will be randomized to one of two diet groups.

Dietary intervention: Participants will be randomized to a HPD (30% protein, 40% carbohydrate, 30% fat) or a NPD (15% protein, 55% carbohydrate, 30% fat) with matched fatty acid profiles and fiber content. The diet will be implemented in two phases: an initial macronutrient standardized diet without calorie restriction for 2 weeks then the same macronutrient standardized diet with 1500 calorie restriction for 14 weeks. Subjects will receive dietary counseling during their baseline visit on their assigned macronutrient standardized diet. After 2 weeks of a macronutrient standardized diet, both groups will then receive further dietary counseling on how to restrict their intake to 1500 calories. Pea-based protein supplements will be provided to the HPD group to achieve the target of 30% calories from protein in the HPD group.

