Nutritional assessments: Participants will complete a three-day food record (3DFR) and the Food Frequency Questionnaire (FFQ) at every study visit to assess adherence to the prescribed macronutrient composition and calorie limit of the two dietary groups. The 3DFR consists of detailed documentation of food eaten on three days. FFQ is a self-administered, semi-quantitative tool that queries the average frequency of consumption over the prior one month of a list of food items. It will be modified to cover only 2 weeks on study visits at weeks 2 and 4. This study will use the Diet History Questionnaire supported by the National Cancer Institute and previously validated against other FFQs. The extensive nutrient composition database that supports the questionnaire allows estimations of the intake of macronutrients (e.g. fats), micronutrients (e.g. carotenoids), and specific food groups such as fruits, vegetables and grains.

B. Measurement of clinical response to the dietary interventions.

Primary and secondary endpoints: The primary clinical endpoint for response to dietary intervention will be weight loss. Secondary measures of clinical response will include change in fat mass, liver steatosis, lipids, and HgbA1c.

Clinical data collection: The following parameters will be obtained on each of 7 study visits: baseline, week 2, week 4, week 6, week 8, week 12, and week 16.

- 1) Physical examination: The study coordinator will measure height, weight, and waist/hip circumference.
- 2) Bioelectrical impedance analysis (BIA): Electrodes attached to a BIA device will be placed on the wrists and ankles. A brief electrical current will be passed to measure resistance and reactance, which can be used to calculate lean body mass and fat mass. One BIA device will be dedicated to this study.
- 3) Liver transient elastography (FibroScan): Hepatic steatosis and fibrosis will be evaluated by transient elastography, a non-invasive test that can be performed in 5 minutes using equipment that will be available down the hall from the clinical research unit where study visits will occur. Steatosis will be assessed by the CAP score and fibrosis by elastography with stiffness measured in kilopascals.

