- 4) Laboratory studies: Blood samples will be collected by venipuncture after 8-14 hours of fasting. Complete blood count, chemistry panel, lipids (total cholesterol, LDL, HDL, triglycerides), and hemoglobin A1c (HgbA1c) will be measured by the clinical laboratory at the West Los Angeles VA Medical Center.

Statistical analysis: Patient characteristics (physical measurements, lean body mass, laboratories, demographic traits) at baseline will be compared using a 2-sided t-test (for numerical variables) or chi-square test (for categorical variables) to evaluate the randomization. 3DFR and FFQ performed at each time point will be used to assess the predicted protein content of the patient's diet compared to baseline to evaluate the success of the dietary intervention. The significance of differences between the two groups in the primary and secondary outcome measures will be assessed using a 2-sided t-test.

C. Kinetic analysis of shifts in microbial composition in obese subjects (BMI 27-40) on a high protein diet compared to an isocaloric normal protein diet.

Fecal sampling: Participants will be provided with kits for home sampling. The subjects will urinate first then defecate into the Fisherbrand Commode Specimen Collection System. Subjects will use a spoon to transfer freshly defecated feces to a Para-Pak stool collection cup prefilled with 95% ethanol to fix the samples, allowing storage at room temperature for up to 2 weeks. Ethanol-fixed and fresh frozen samples give comparable metagenomics results to samples stored in preservatives such as RNALater while minimizing subjects' risk of exposure to toxic chemicals. The remaining feces will be frozen. This involves removing the cup from the

toilet hat, tightly closing the lid, and transferring the cup to a Ziploc bag for storage in the subject's freezer. Frozen samples will be delivered to the VA clinic during scheduled study visits using a Styrofoam box containing U-tek freezer packs designed to maintain a temperature of -20°C as was performed for a recent study. Reminder calls will be made 4 days before each study visit. Subjects who forget to bring in samples will be asked to either bring them in at the next visit or send them via overnight FedEx delivery. Samples will be stored at -80°C.

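### The model that tests diet by time point for each bacterium may be adjusted for post-baseline intake, which is the randomised diet as received

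*Combined protocol and SAP*

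**What the plan says.** All references are to the combined protocol and SAP.

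- **Section C, Microbiome analysis.** The model for each bacterium contains diet group, time point, their interaction, baseline BMI, age, sex and smoking status. The plan then adds: "Diet composition parameters derived from the nutritional instruments (3DFR, FFQ) may also be included". Next comes the test: "This model will be compared to a reduced model that does not include the diet:time point interaction". Its purpose is given as: "A likelihood ratio test will be used to identify microbes with differential abundance by diet at time points after baseline". Significance is q below 0.05.
- **Section A, Dietary intervention.** The arms are "HPD (30% protein, 40% carbohydrate, 30% fat) or a NPD (15% protein, 55% carbohydrate, 30% fat) with matched fatty acid profiles and fiber content".
- **Section A, Nutritional assessments.** Both instruments are completed "at every study visit to assess adherence to the prescribed macronutrient composition and calorie limit of the two dietary groups".
- **Section B, Statistical analysis.** "3DFR and FFQ performed at each time point will be used to assess the predicted protein content" of the diet relative to baseline, as a check that the intervention worked.
- **Section A, Rationale and hypothesis.** The hypothesis is that "a high protein diet will shift the composition of the microbiome of obese subjects, including increased" *Akkermansia*.

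BMI is explicitly a baseline value. The optional intake terms carry no such label, and no nutrient, visit, instrument or analysis role (main or supportive) is named for them.

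**The concern.** Protein and carbohydrate shares are what the trial randomises. Once the diets start, a participant's recorded protein or carbohydrate intake is the assigned treatment as received. It is not a background characteristic to be adjusted away. A term for it would sit in both models being compared, so the interaction could be credited only with the diet effect that recorded intake leaves unexplained. That is a different question from the stated one.

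This is the only stated test of individual bacteria, and the hypothesis names one. A real shift acting through the randomised nutrient could be underestimated or missed, and a null adjusted result could be misread as no effect of diet. If intake and a bacterium also share unmeasured causes, conditioning on post-randomisation intake gives up the protection of randomisation, and the bias can go in either direction.

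**Working it through.** **Plan's own figure.** There is none to reproduce. The plan gives "an estimated 216 obese Veterans assigned 1:1 to isocaloric high protein (HPD) or normal protein (NPD) diets", so 216 / 2 = 108 per arm, but no effect size, dispersion or power for any bacterium.

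**Inputs from the documents.** Protein is 30% against 15%, a contrast of 15 points. Carbohydrate is 40% against 55%, also 15 points. Fat is 30% in both arms. Intake is recorded at 7 visits and stool is collected at 11 time points.

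**Inputs assumed.** The share m of the diet effect that acts through the intake; the within-arm SD of true intake; the SD of reporting error (taken as equal in the two arms); and a mean baseline protein share equal in the two arms.

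**Step 1: share removed.** Let the diet-by-time effect on the log scale be T, with mT acting through protein.

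- The slope per protein point is mT / 15.
- With measured intake, that slope is shrunk by the within-arm reliability R = SD_true² / (SD_true² + SD_error²).
- The covariate absorbs (mT / 15) × R × 15 = mRT.
- The remaining interaction is T(1 − mR), so the share removed is m × R. The 15-point contrast cancels.

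**Step 2: assumed illustration, m = 1, same-visit records, within-arm SD 4.**

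| Reporting error SD | R = share removed | A 2.05-fold shift is estimated as |
|---|---|---|
| 3 | 16 / (16 + 9) = 0.64 | 2.05^0.36 = 1.29 |
| 5 | 16 / (16 + 25) = 0.39 | 2.05^0.61 = 1.55 |

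Seven-visit negative binomial simulations with 108 per arm and dispersion 1 gave 1.28 to 1.33 and 1.53 to 1.57, in agreement.

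**Step 3: wider range of reliability.** Simulated 2-fold shift, seven visits, 200 runs per cell, other assumptions as above:

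| R | Share removed, m = 1 | Share removed, m = 0.5 |
|---|---|---|
| 0.2 | 21% | 10% |
| 0.4 | 39% | 20% |
| 0.7 | 69% | 34% |
| 1.0 | 99% | 49% |

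These track m × R.

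**Step 4: power, illustrative only.** The simulations treat repeated samples as independent and the dispersion as known, so only the direction carries over to the trial.

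- *Wholly through protein.* In the Step 3 setting, for one bacterium at a nominal 0.05, power fell from 0.97 to 0.45 at R = 0.4 and to 0.16 at R = 0.7.
- *Not through protein.* For a 2.05-fold shift over seven visits, at a cut-off of p < 0.004, the estimate was unchanged. Power still fell from 86–88% to 71–74%, because intake is strongly correlated with the interaction.
- *Large shifts.* With 11 time points and q < 0.05, a rapid 3.5-fold shift wholly through protein fell from 100% to 7–80% when each sample took the next visit's record. It stayed at 96% or more when intake was interpolated or the last record was carried forward.

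**Step 5: matching intake to stool samples.** Stool at days 3, 7, 17 and 21 has no same-day visit record. Section A (Nutritional assessments) shortens the FFQ to 2 weeks at weeks 2 and 4. Those windows run from day 0 to 14 and from day 14 to 28, so they cover the four samples as intervals. The plan does not say how intake would be assigned to them.

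**The case against.** The strongest reply is that this is a permission and not a commitment. Harm needs three choices that the plan never makes: to use the option, to use post-baseline values, and to choose an intake variable that the diets move. The examples of instrument output in section A are fats, carotenoids and food groups, not protein. A reader might infer that the trial intends to adjust for on-study protein; the text does not say so. This stands, and it is why the point is conditional.

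A second reply is that the size is assumed. This also stands: reliability, mediated share, dispersion and effect size are all absent from the documents. A reader might take from the illustration that most of the effect will be lost. That requires m × R above one half; at a reporting error SD of 5 the loss is 39% even for a wholly mediated effect.

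A third reply is that some intake terms are harmless. Baseline intake is. Nutrients matched by design should do little harm if actual intake also matches, but matching on prescription does not guarantee that. A 40% against 55% carbohydrate prescription may also shift food groups such as grains and fruit. A bar on protein and carbohydrate alone would therefore be too narrow.

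None of these replies removes the gap: the permission covers post-baseline intake, and the model it enters is the one used for the test.

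**Conclusion.** The point holds in conditional form. The plan allows post-baseline intake into the model that tests diet by time point. If that option is used, above all with protein or carbohydrate, the test no longer estimates differential abundance by randomised diet.

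The transferable result is a loss of about m × R of the effect, under simple mediation with same-visit records. The 39–64% loss for a wholly mediated shift rests on the assumed within-arm SD of 4 and error SD of 3 to 5. Effects that do not act through intake keep an unbiased estimate in this setting but lose some power. Large shifts can also lose power under some rules for assigning intake to samples.

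Two stronger readings are not supported. A reader might infer that intake is wholly unrecorded around days 3, 7, 17 and 21; the 2-week FFQ covers those intervals. A reader might also extend the problem to the rest of the analysis. The t-tests of weight loss and the other clinical outcomes, the alpha diversity comparisons and Adonis have no stated intake adjustment and are not affected.

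This should be changed: the harm is conditional, but it falls on the test of the trial's named microbial hypothesis.

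**What to change.** Replace the optional sentence in section C (Microbiome analysis) with:

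> The model testing diet:time point will include only baseline covariates; baseline 3DFR/FFQ intake may be added. No post-baseline intake variable will be included in that model. Associations of post-baseline intake with taxa will be reported in a separate, labelled exploratory analysis.

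If the exploratory analysis uses all 11 stool samples, it should also state how intake is assigned to days 3, 7, 17 and 21.

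The cost is small: SAP wording only, no new data and no change to the conduct of the trial. The downside is that the intake-adjusted result becomes exploratory only.
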